9.3. SERIOUS ADVERSE EVENT (SAE)

9.3.1. Definitions

The SAE definition and reporting requirements are in accordance with the ICH Guideline for Clinical Safety Data Management: Definitions and Standards for Expedited Reporting, Topic E2A.

An SAE is any AE occurring at any dose that:

- o Results in death.
- o Is immediately life-threatening (ie, in the opinion of the investigator, the AE places the subject at immediate risk of death; it does not include a reaction that, had it occurred in a more severe form, might have caused death).
- o Requires inpatient hospitalization or results in prolongation of an existing hospitalization.
- o Results in significant incapacity or substantial disruption of the ability to conduct normal life functions.
- o Is a congenital anomaly or birth defect.

- o Is an important medical event that may not be immediately life-threatening, result in death, or require hospitalization, but may be considered an SAE when, based upon appropriate medical judgment, it jeopardizes the subject or may require medical or surgical intervention to prevent one of the outcomes listed above.

9.3.2. SAE Reporting

As soon as an investigator becomes aware of an AE that meets the criteria for an SAE, the investigator will document the SAE to the extent that information is available.

SAEs, regardless of causal relationship, must be reported to the Sponsor or designee within 24 hours of the investigator's knowledge of the event by submitting the completed SAE report form and any other pertinent SAE information as indicated on the SAE Reporting form (or in the SAE Reporting form Completion Guidelines) and confirming the report was received. Forms for reporting SAEs and contact information will be provided to the study sites.

Reporting Information for safety reports

To report initial or follow-up information to Ipsen/Roche, a completed Clinical Study Serious Adverse Event (SAE) report form should be sent to the following within 24 hours of becoming aware of the event:
 
Serious Adverse Events
 
All serious adverse events must be reported by fax within 24 h to MFAR Clinical Research, S.L.
 
by fax ([name]) or e-mail to [contact]

SAEs that must be recorded on an SAE Reporting form include the following:

- All SAEs that occur after informed consent and through 100 days after the date of the decision to permanently discontinue study treatment (ie, the later of the date of the decision of the investigator to permanently discontinue study treatment or the date of the last dose of any study treatment taken by the subject) or the date the subject is deemed to be a screen failure.
- Any SAEs assessed as related to study treatment or study procedures, even if the SAE occurs more than 100 days after the date of the decision to permanently discontinue study treatment.

Note: If the subject does not meet the eligibility criteria during screening, then SAEs only need to be reported from the time the subject signs the informed consent until the day when the subject has been determined to not be eligible for study participation.

SAEs that occur after the initiation of study treatment through 100 days after the date of the decision to permanently discontinue of study treatment must also be recorded on the CRF page.

The minimum information required for SAE reporting includes identity of Investigator, site number, subject number, and an event description. Other important information requiring timely reporting are the SAE term(s), the reason why the event is considered to be serious (ie, the seriousness criteria), and the Investigator's assessment of the relationship of the event to study treatment. Additional SAE information including medications or other therapeutic measures used to treat the event, action taken with the study treatment because of the event, and the outcome/resolution of the event will be recorded on the SAE form.

In all cases, the Investigator should continue to monitor the clinical situation and report all material facts relating to the progression or outcome of the SAE. Furthermore, the Investigator may be required to provide supplementary information as requested by the Sponsor's Drug Safety personnel or designee.

When reporting SAEs, the following additional points will be noted:

- When the diagnosis of an SAE is known or suspected, the Investigator will report the diagnosis or syndrome as the primary SAE term, rather than as signs or symptoms. Signs and symptoms may then be described in the event description.
- Death will not be reported as an SAE, but as an outcome of a specific SAE, unless the event preceding the death is unknown. Terms of “Unexplained Death” or “Death from unknown origin” may be used when the cause is unknown. In these circumstances the cause of death must be investigated and the diagnosis amended when the etiology has been identified. If an autopsy was performed, the autopsy report should be provided.
- While most hospitalizations necessitate reporting of an SAE, some hospitalizations do not require SAE reporting, as follows:
 - Elective or previously scheduled surgeries or procedures for preexisting conditions that have not worsened after initiation of treatment (eg, a previously scheduled ventral hernia repair). SAEs must, however, be reported for any surgical or procedural complication resulting in prolongation of the hospitalization.
 - Prespecified study hospitalizations for observation.
 - Events that result in hospital stays of fewer than 24 hours and that do not require admission (eg, an emergency room visit for hematuria that results in a diagnosis of cystitis and discharge to home on oral antibiotics).
- SAEs must be reported for any surgical or procedural complication resulting in prolongation of the hospitalization.

9.3.2. SAE Regulatory Reporting

The Sponsor’s Drug Safety group (or designee) will process and evaluate all SAEs and AESIs as the reports are received. For each SAE received, the Sponsor will make a determination as to whether the criteria for expedited reporting to relevant regulatory authorities have been met.

The Sponsor’s Drug Safety group (or designee) will assess the expectedness of each SAE to the study treatment using the current reference safety information (RSI) for each study drug. RSI for this trial will be the last version of study treatment Investigator Brochure. If information on the expectedness has been made available by the reporting investigator, this should be taken into consideration by Sponsor. If Sponsor disagrees with the investigator’s expectedness assessment, both the opinion of the investigator and the sponsor should be provided in the report.

The Sponsor or its designee is responsible for reporting relevant SAEs to the relevant regulatory authorities, and participating investigators, in accordance with FDA regulations (21 Code of Federal Regulations [CFR] 312.32), ICH guidelines, European Clinical Trials Directive (Directive 2001/20/EC), and/or local regulatory requirements.

Reporting of SAEs by the Investigator to his or her IRB/ECs will be done in accordance with the standard operating procedures and policies of the IRB/EC. Adequate documentation must be maintained showing that the IRB/EC was properly notified.

MFAR Clinical Research on behalf of GETNE will forward safety reports received to both IPSEN and ROCHE within one working day, following agreed procedures (signed IPSEN agreement and ROCHE SDEA) in order they can fulfill the corresponding legal requirement regarding pharmacovigilance as MAH of cabozantinib and atezolizumab respectively.

All adverse events will be processed by MFAR/Ipsen/Roche according to their relevant Standard Operating Procedures. This includes the follow up of adverse event reports with the Investigator through MFAR Clinical Research, as required. If an AE occurs with a “non Ipsen/Roche product”, the Investigator should

consider informing the competent authority in the Member State where the event occurred or to the marketing authorisation holder of the suspected medicinal product, but not to both (to avoid duplicate reporting).

The Sponsor through MFAR Clinical Research ensures that the reporting requirements and timelines for reporting, as defined in the respective applicable laws, are followed. A Development Safety Update Report (DSUR) will be provided to the local investigators for filing into the investigator's file. MFAR Clinical Research will submit the DSUR to the involved ECs and involved Regulatory Agencies.

9.4. ADVERSE EVENTS OF SPECIAL INTEREST

Adverse events of special interest (AESIs) consist of immune-mediated AEs associated with ICIs, cases of potential DILI, and suspected transmission of an infectious agent by the study treatment (Table 3).

AESIs will be reported to the Sponsor or designee using the SAE reporting form irrespective of whether the event is serious or nonserious; all AESIs must be reported within 24 hours using the SAE process as described in Section 9.3.

Guidance for management of immune-mediated AEs associated is provided in Investigator's Brochure for atezolizumab.

Table 3. Adverse Events of Special Interest

Category	Event
DILI	
Cases of potential Drug-induced Liver Injury (DILI) that include an elevated ALT or AST in combination with either an elevated bilirubin or clinical jaundice, as defined by Hy's Law and based on the following observations:
Treatment-emergent ALT or AST $> 3 \times$ baseline value in combination with total bilirubin $> 2 \times$ ULN (of which $\geq 35\%$ is direct bilirubin).Treatment-emergent ALT or AST $> 3 \times$ baseline value in combination with clinical jaundice.
Other	
Suspected transmission of an infectious agent by the study treatment, as defined below:
Any organism, virus, or infectious particle (eg, prion protein transmitting transmissible spongiform encephalopathy), pathogenic or non-pathogenic, is considered an infectious agent. A transmission of an infectious agent may be suspected from clinical symptoms or laboratory findings that indicate an infection in a patient exposed to a medicinal product. This term applies only when a contamination of study treatment is suspected.
irAE	
Systemic lupus erythematosus
irAE	
Events suggestive of hypersensitivity, infusion-related reactions, cytokine release syndrome, HLH and MAS
irAE	
Nephritis
irAE	
Ocular toxicities (eg, uveitis, retinitis)
irAE	
\geq Grade 2 cardiac disorders (eg, atrial fibrillation, myocarditis, pericarditis)
irAE	
Vasculitis
irAE	
Autoimmune hemolytic anemia

irAE	
 Severe cutaneous reactions (e.g., Stevens-Johnson syndrome, dermatitis bullous, toxic epidermal necrolysis)
------	---

ALT, alanine aminotransferase; AST, aspartate aminotransferase; DILI, drug-induced liver injury; irAE, immune-related adverse event; ULN, upper limit of normal.

9.4.1 General Information on Immune-Related Adverse Events

The immune-modulating properties of checkpoint-inhibitors, such as the anti-PD-L1 antibody atezolizumab, are able to unbalance immunologic tolerance and generate a subset of AEs (called irAEs) with an autoimmune inflammatory pathomechanism. Immune-related adverse events may involve any organ or tissue (Michot et al 2016). Most irAEs occur within the first 12 weeks of exposure to ICIs but some of them may appear with a delayed onset. Diagnosis of irAEs should be based on exposure to an ICI and a reasonable immune-based mechanism of the observed AE. Whenever possible, histologic examination or other immune-based diagnostic evaluations should be used to support the diagnosis. Other etiologic causes including AEs from tumor progression should be ruled out.

The spectrum of irAEs is wide and can be general or organ-specific. Examples of general irAEs in subjects treated with ICIs are fatigue, fever, and chills. Organ-specific irAEs consist of dermatitis (rash, pruritus, vitiligo, oral mucositis, and gingivitis), enterocolitis (diarrhea with abdominal pain and clinical or radiological evidence of colonic inflammation), and endocrinopathies (pituitary, thyroid, adrenal, testes). Diagnosis of endocrine dysfunction is challenging with relatively nonspecific symptoms. Additional laboratory testing of the endocrine axes may be helpful: prolactin (pituitary-hypothalamic function), FT4 and TSH (pituitary-thyroid function), luteinizing hormone (LH) and follicle-stimulating hormone (FSH; pituitary-gonadal function), adrenocorticotrophic hormone (ACTH) and cortisol (pituitary-adrenal function).

Additional organ-specific irAEs include hepatitis (AST/ALT increases, hepatomegaly, periportal edema, periportal lymphadenopathy, lymphocyte infiltrates periportal and surrounding primary biliary ducts) and pneumonitis (acute interstitial pneumonia). Less frequent irAEs include neurologic syndromes (myasthenia gravis, Guillain-Barré syndrome, aseptic meningitis), ocular AEs (uveitis), renal AEs (interstitial nephritis), cardiac AEs (myocarditis), muscular AEs (myositis), and pancreatic AEs (lipase increase).

9.5. FOLLOW-UP OF ADVERSE EVENTS

Non-serious AEs are to be recorded in the CRF until 30 days after the date of the decision to discontinue study treatment (the later of the date of the decision by the investigator to permanently discontinue study treatment or the date of the last dose of any study treatment taken by the subject). The status of unrelated SAEs that are ongoing after the date of the decision to discontinue study treatment will be documented as of the 100-day FU-2 visit.

All AESIs (regardless of seriousness) and all related SAEs that are ongoing 100 days after the date of the decision to discontinue study treatment (the later of the date of the decision by the investigator to permanently discontinue study treatment or the date of the last dose of any study treatment taken by the subject), and AEs assessed as related that led to study treatment discontinuation that are ongoing 100 days after the date of the decision to discontinue study treatment, are to be followed until either:

- the AE has resolved
- the AE has improved to Grade 2 or lower
- The Investigator determines that the event has become stable or irreversible.

Further details on follow-up procedures are summarized in section 8.1 study determinations chart.

9.6. OTHER SAFETY CONSIDERATIONS

9.6.1. Pregnancy

Use of highly effective methods of contraception is very important during the study and for 5 months after the last dose of study treatment. If a subject becomes pregnant during the study, she will be taken off study treatment. She will be followed through the end of her pregnancy and the infant should have follow up for at least 6 months after birth. Furthermore, male subjects are required to use condoms in order to avoid transmission of study treatment in semen for 5 months after their last dose of study treatment. If a female partner of a male subject becomes pregnant during the study, the Sponsor will ask the pregnant female partner to be followed through the end of her pregnancy and for the infant to be followed for at least 6 months after birth. Both male and female subjects should seek advice and consider fertility preservation before receiving study treatment.

The Investigator must inform the Sponsor of the pregnancy. Forms for reporting pregnancies will be provided to the study sites upon request. The outcome of a pregnancy (for a subject or for the partner of a subject) and the medical condition of any resultant offspring must be reported to the Sponsor or designee. Any birth defect or congenital anomaly must be reported as an SAE and any other untoward events occurring during the pregnancy must be reported as AEs or SAEs, as appropriate.

Females should not breastfeed while receiving study treatment and for the following periods after discontinuing study treatment:

- **Combination cabozantinib plus atezolizumab:** at least 5 months from the last dose of atezolizumab or 4 months from the last dose of cabozantinib, whichever is later
- **Single-agent cabozantinib:** at least 4 months from the last dose of cabozantinib
- **Single-agent atezolizumab:** at least 5 months from the last dose of atezolizumab

9.6.2. Medication Errors/Overdose/Drug abuse/Drug misuse

Medication error is defined as accidental deviation in the administration of a drug (e.g. wrong dose administered, wrong dosing schedule, incorrect route of administration, wrong drug, expired drug administered). In some cases, a medication error may be intercepted prior to administration of the drug.

Any study medication overdose, misuse, abuse, or study medication error (excluding missed doses) that results in an AE or SAE requires reporting to the Sponsor or designee according to the guidance for AE and SAE reporting (Sections 9.1 and 9.2, respectively).

In case of overdose, the Coordinating Investigator or designee should be contacted promptly to discuss how to proceed. Any AEs that occur as a result of an overdose have to be treated according to clinical standard practice.

Please refer to the Investigator's Brochure for additional management recommendations for an overdose of cabozantinib and/or atezolizumab.

In addition, all study medication overdose, misuse, abuse or medication error, regardless of whether they result in an adverse event, should be recorded on the Adverse Event CRF

9.6.2 Lack of Efficacy or Worsening of study disease:

Events that are clearly consistent with the expected pattern of progression of the underlying disease should not be recorded as adverse events. These data will be captured as efficacy assessment data only. In most cases, the expected pattern of progression will be based on RECIST v1.1 criteria. In rare cases, the

determination of clinical progression will be based on symptomatic deterioration. However, every effort should be made to document progression through use of objective criteria. If there is any uncertainty as to whether an event is due to disease progression, it should be reported as an adverse event.

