9.2.1.1. Adverse Event (AE)

An AE is any untoward medical occurrence in a patient or clinical investigation subject administered a medicinal product and that does not necessarily have a causal relationship with this treatment. An AE can therefore be the development of a new medical condition, or the deterioration of a pre-existing medical condition. This includes any unfavorable and unintended sign (e.g. tachycardia, enlarged liver), symptom (e.g. nausea, chest pain) or the abnormal results of an investigation (e.g. laboratory findings, electrocardiogram) temporally associated with the use of a medicinal product, whether or not considered related.

This requirement includes specific events or symptoms associated with cancer progression or general clinical deterioration to ensure potential toxicities are not overlooked. Radiographic progression without associated clinical sequelae is not considered an AE; terms such as 'disease progression' should be avoided. Pre-existing medical conditions that worsen during a study will be recorded as AEs. Abnormal laboratory values, ECG findings, or vital signs are to be recorded as AEs if they meet the criteria described in Section 9.3.

All untoward events that occur after informed consent through 30 days (100 days for SAEs and AESIs) after the date of the decision to permanently discontinue study treatment (defined as the later of the date of the decision to discontinue all study treatment or the date of the last dose of any study treatment) are to be recorded by the investigational site.

At each scheduled and unscheduled visit, AEs are to be identified and assessed based upon study procedures, routine and symptom-directed clinical investigations, and subject query/report.

Assessment of the relationship of the AEs to study treatment by the investigator will be based on the following two definitions:

- Not Related: An event is assessed as not related to study treatment if it is attributable to another cause and/or there is no evidence to support a causal relationship.
- Related: An event is assessed as related to study treatment when there is a reasonable possibility that study treatment caused the event. Reasonable possibility means there is evidence to suggest a causal

relationship between study treatment and the event. This event is called a suspected adverse reaction. A suspected adverse reaction implies a lesser degree of certainty about causality than adverse reaction, which means any AE caused by a drug.

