10.5. SAFETY ANALYSIS

The safety population (SP) consists of all enrolled subjects who received at least one dose of study treatment. Patients will be monitored for safety during all the stages of the study. All safety and tolerability assessments will be done at pre-dosing time, unless otherwise specified.

Assessment of adverse events, safety, and toxicity will be performed according to the National Cancer Institute Common Toxicity Criteria (version 5.0) from the time of Informed Consent for the pre-registration phase until the end of study. Safety and tolerability of study medication will be determined by evaluating the type, incidence, frequency, severity, seriousness and causality of adverse effects. Physical examinations, and laboratory tests will also be assessed. Any signs and/or symptoms associated with the worsening of the existing tumour at baseline (in severity or frequency) during the trial should be reported as adverse event.

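### Clear, symptomatic progression is an AE under protocol 9.2.1.1 and 10.5 but is not to be recorded under the second 9.6.2, so all-cause grade 3 or higher and SAE counts depend on which section a site follows; the AE recording period is also inconsistent

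*Combined protocol and SAP*

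**What the plan says.** Three protocol sections address whether progression is an adverse event.

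- Section 9.2.1.1, after defining an AE, adds: "This requirement includes specific events or symptoms associated with cancer progression or general clinical deterioration to ensure potential toxicities are not overlooked". Its one exemption is "Radiographic progression without associated clinical sequelae is not considered an AE".
- Section 10.5 says that signs or symptoms tied to "worsening of the existing tumour at baseline (in severity or frequency) during the trial should be reported as adverse event".
- The second section numbered 9.6.2 says: "Events that are clearly consistent with the expected pattern of progression of the underlying disease should not be recorded as adverse events". Such events are to be held as efficacy data. It continues: "In most cases, the expected pattern of progression will be based on RECIST v1.1 criteria", and adds that, rarely, the "determination of clinical progression will be based on symptomatic deterioration". It closes with: "If there is any uncertainty as to whether an event is due to disease progression, it should be reported as an adverse event".

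Section 9.3.1 begins its definition with "An SAE is any AE occurring at any dose that" and then lists the seriousness criteria.

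The recording period is also described in several ways.

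- Section 9.2.1.1 runs from consent to 30 days after permanent discontinuation, or 100 days for SAEs and AESIs. Section 9.5 repeats the 30 days for non-serious AEs and refers to a 100-day visit called FU-2.
- Sections 8.2.2 and 8.2.3 have AEs graded and recorded through follow-up. Sections 9.2.1.2 and 10.5 describe assessment from consent to end of study.
- The opening of section 9 sends sites to Table 2. Its AE row is marked from cycle 1 to end of treatment only, and it has no column for FU-2.
- Protocol 10.6 and SAP 1.5 count an AE as treatment-emergent up to study completion.
- Section 9.3.2 (SAE reporting) also requires related SAEs beyond 100 days, and 7.2.2 makes autoimmune disease an SAE at any time after treatment stops.

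**The concern.** A site that follows 9.6.2 leaves out events that a site following 9.2.1.1 or 10.5 enters. The omission carries through: what is not an AE cannot be an SAE or a grade 3 or higher AE. The SAP tables for those counts carry no rule on progression, so nothing at analysis evens out the difference. The trial is single-arm, so there is no concurrent control group subject to the same recording practice. Some per-cohort tables may rest on nine patients.

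The recording period raises a smaller problem. If the treatment-emergent window is open to study completion but required recording of non-serious AEs ends at 30 days, late non-serious AEs reach the tables only from sites that keep recording.

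**Working it through.** The plan states no figure on this point to reproduce, so the check is mainly a comparison of texts.

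**1. Where the sections disagree**

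| Event | 9.2.1.1 | 10.5 | Second 9.6.2 |
|---|---|---|---|
| Progression on scan, no clinical consequences | Not an AE | Not addressed (concerns signs and symptoms) | Not an AE |
| Symptoms, cause uncertain | AE | AE if tied to the tumour | AE |
| Symptoms, clearly expected progression | AE | AE | Not recorded |

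Only the last row conflicts, and no section takes precedence.

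**2. Which outputs move**

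Table numbers are those in the body of the SAP; its index numbers them differently.

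- Affected: the all-cause grade 3 or higher AE and SAE rows of Tables 190 and 206, the term-level Tables 200, 202, 212 and 213, and listings 201 and 203.
- Treatment-related tables: clear progression would be judged not related under 9.2.1.1, so these barely change.
- ORR and PFS come from RECIST assessments, and OS counts death from any cause. None depends on AE recording.

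**3. Size per patient**

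One patient with no other qualifying event shifts a row by 100/n percentage points. Cohort sizes 9 and 24 are from protocol 10.1; totals 54 and 144 are from the synopsis.

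- 100/9 = 11.1
- 100/24 = 4.2
- 100/54 = 1.9
- 100/144 = 0.7

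These are planned numbers. The safety population needs at least one dose, so actual denominators may be slightly smaller.

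**4. An assumed range**

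The documents give no rate for clear symptomatic progression. Suppose a share b of patients has another grade 3 or higher AE, and a share q, independently, has clear symptomatic progression of grade 3 or higher. If all sites used one rule rather than the other, the row would differ by (1 − b) × q.

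- b = 60%, q = 5%: 0.40 × 0.05 = 2 points
- b = 40%, q = 30%: 0.60 × 0.30 = 18 points

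Both inputs are assumptions. With sites split between the rules, the result lies between the two.

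**5. The recording period, by example**

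Take the last patient enrolled, stopping treatment at the first scheduled scan (week 12, protocol 10.3). Read study completion as last patient last visit, 12 months after last enrolment (6.5).

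- Non-serious AEs that are not AESIs: 84 + 30 = day 114, leaving 365 − 114 = 251 days of the treatment-emergent window without required recording under 9.2.1.1 and 9.5.
- SAEs and AESIs: 84 + 100 = day 184, leaving 365 − 184 = 181 days. Even then, related SAEs and autoimmune events remain reportable.
- A patient still on treatment at last patient last visit: no gap.

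**The case against.** The strongest reply is that the sections can be read together: do not enter progression itself as an AE, but do enter its symptoms. Section 9.2.1.1 discourages disease progression as an AE term, and 9.6.2 mentions symptomatic deterioration only as a rare way of determining progression. This may well be what was intended. It is not what 9.6.2 says: it excludes events, not a term, and it extends to progression recognised by symptoms. Its uncertainty clause covers only uncertain cases.

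Other objections stand in part.

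- The documents do not show that sites differ. A reader might infer that they do, but one CRO monitors them and receives the SAEs, and may impose one reading. The contradiction creates the possibility only.
- Omitted events are not wholly lost. They can be queried, and 6.3 asks for cause of death to be documented. They are still absent from the AE dataset unless someone looks.
- On the period, 9.2.1.2 and 10.5 can be read as describing CTCAE grading, and an open treatment-emergent window can hold whatever is collected. That does not settle 8.2.2 and 8.2.3, which say AEs are recorded through follow-up, or the missing FU-2 column.

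**Conclusion.** The recording rule is wrong as written for one class of event: clear, symptomatic progression. The consequence is confined to a descriptive secondary endpoint, namely the all-cause grade 3 or higher and SAE counts and their listings. Its frequency is unknown. The per-patient shift of 11.1 to 0.7 points assumes a patient with no other qualifying event in that row, and the 2 to 18 point range rests on assumed rates.

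A reader might infer that the safety or efficacy conclusions are compromised. The documents do not support that, for the reasons in step 2 of the check.

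A reader might also take the 251 days as time without any safety collection. It applies only to non-serious AEs that are not AESIs, in one assumed patient. Nor is the gap always longer for patients enrolled earlier, since it depends on when each stops treatment. Section 9.2.1.1 already contains a workable tiered period. The secondary fault is that other sections, Table 2 and the treatment-emergent definition do not match it.

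This should be corrected. Confidence is high on the textual conflict and limited on its practical size.

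**What to change.** **Recording rule.** Reconcile 9.2.1.1, 10.5 and the second 9.6.2 into one rule, and renumber the latter. One option is the rule already in 9.2.1.1 and 10.5: record symptoms and clinical consequences of progression as AEs with causality, and do not record progression seen only on a scan. Recorded events can be set aside at analysis; unrecorded ones must be sought by query. Flag progression-related events in the AE dataset and show the all-cause AE, grade 3 or higher and SAE tables with and without them.

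**Period.** Bring 8.2.2, 8.2.3, section 9, 9.2.1.2, 9.5, 10.5 and Table 2 into line with the tiers in 9.2.1.1. Keep the later requirements for related SAEs (9.3.2) and autoimmune events (7.2.2). Add the 30-day and 100-day contacts to Table 2. Align the treatment-emergent definition in 10.6 and SAP 1.5 with the same tiers and list later events separately. A single 30-day cut would be a poor choice: it would move day 31 to 100 SAEs and AESIs out of the main tables, although 7.2.3 and 9.4.1 warn that immune-mediated events can appear late.

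**Cost.** Wording changes, one dataset flag, one extra set of tables and a memo to sites. Enrolment began on 08/10/2020, so events already left unrecorded under 9.6.2 must be queried or acknowledged as a limitation.
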